4.10.2. Adverse Events

4.10.2.1. Adverse Events

Adverse events are recorded in the eCRF. Each AE will be coded to System Organ Class (SOC) and Preferred Term (PT), using the *Medical Dictionary for Regulatory Activities* (MedDRA) version that is current at the time of database lock. Severity of AEs is recorded as mild, moderate, or severe.

A treatment-emergent adverse effect (TEAE) is defined as an event that first occurs or worsens in severity after baseline, with baseline defined as all preexisting conditions recorded at Visit 1 and any AEs recorded before the first dose of study intervention (that is, between Visits 1 and 2 and recorded with the time of onset before the first dose of study intervention) and up to 30 days after study treatment discontinuation. The MedDRA Lowest Level Term (LLT) will be used in defining which events are treatment-emergent. The maximum severity for each LLT during the baseline period until the first dose of the study medication will be used as baseline. While unusual, it is possible to have a missing severity for events. For events with a missing severity during the baseline period, the event will be treated as mild in severity for determining treatment-emergence. Events with a missing severity during the postbaseline period will be treated as

severe and treatment-emergence will be determined by comparing with baseline severity. For events occurring on the day of the first dose of study treatment, the day and time of the onset of the event will both be used to distinguish between pretreatment and posttreatment in order to derive treatment-emergence. Note that conditions with a partial or missing start date will be assumed to be "not preexisting" unless there is evidence, through comparison of partial dates, to suggest otherwise. Patients will only be counted once if same PT is listed in 2 or more different SOC categories.

The planned summaries for AEs are provided in Table 4.2. For events that are gender-specific, the denominator and computation of the percentage will only include participants from the given gender. MedDRA PTs are assigned to a SOC through primary mappings (as defined by MedDRA). Thus, MedDRA PTs will appear in only 1 SOC. Unless otherwise specified, the planned summaries for AEs will be provided for the treatment period. A listing of AEs that occur more than 30 days after study treatment discontinuation will also be provided.

Table 4.2. Summary Tables Related to Adverse Events

Analysis	Details

MedDRA = Medical Dictionary for Regulatory Activities; PT = Preferred Term; SAE = serious adverse event; SOC = System Organ Class; TEAE = treatment-emergent adverse event.

4.10.2.2. Serious Adverse Events

According to the ICH E2A guideline, an SAE is any AE that results in 1 of the following outcomes:

- death
- initial or prolonged inpatient hospitalization
- a life-threating experience (that is, immediate risk of dying)
- persistent or significant disability/incapacity
- congenital anomaly/birth defect, or
- considered significant by the investigator for any other reason.

The number and percentage of patients who experienced any ICH-defined SAE will be summarized by treatment group during the treatment and follow-up periods using the MedDRA PT nested within the SOC. An individual listing of all SAEs will be provided.

4.10.2.3. Adverse Events of Special Interest (AESI)

AESI are considered an intervention-specific topic and will be described in the respective ISA SAPs/appendices.

4.10.3. Clinical Laboratory Evaluations

All laboratory tests will be presented using the Système International of units (SI) and United States conventional (CN) units. For topics of safety in special groups and circumstances, laboratory test units will be specified for each analysis. Central laboratory reference ranges will be used.

The following will be conducted for laboratory analyte measurements collected quantitatively:

Box plots for observed values

Values at each visit (starting at randomization) and change from baseline to each visit and to last postbaseline measure will be displayed in box plots for patients who have a baseline and at least 1 postbaseline visit. For visits included in the treatment period, patients will be included only if the visit occurs on or before the date of treatment discontinuation or completion. The follow-up visit will be the first visit that occurred during the follow-up period. Individual measurements outside of the reference limits will also be displayed using distinct symbols overlaying the box plot. Original-scale data will be used for the display but for some analytes (for example, immunoglobulins) a logarithmic scale will be used to aid in viewing measures of central tendency and dispersion. Unplanned measurements will be excluded. Descriptive summary statistics will be included in a table below the box plot. These box plots will be used to evaluate trends over time and to assess the potential impact of outliers on central tendency summaries. No inferential statistics will be provided.

• Treatment-emergent high/low analyses

The number and percentage of patients with treatment-emergent high and low laboratory results at any time will be summarized by treatment conditions. Planned and unplanned measurements will be included. A treatment-emergent high result is defined as a change from a value less than or equal to the high limit at all baseline visits, to a value greater than the high limit at any time

during the treatment period, and up to 60 days after treatment discontinuation. A treatmentemergent low result is defined as a change from a value greater than or equal to the low limit at all baseline visits, to a value less than the low limit at any time during the treatment period, and up to 60 days after treatment discontinuation. No inferential statistics will be provided.

Listing of abnormal findings

A listing of abnormal findings for laboratory analytes will be provided. The listing will include, but is not limited to, patient identification (ID), treatment group, laboratory collection date, analyte name, and analyte finding.

4.10.3.1. Abnormal Hepatic Tests

Analyses for abnormal hepatic tests involve 4 laboratory analytes: alanine aminotransferase (ALT), aspartate transaminase (AST), total bilirubin (TBL), and serum alkaline phosphatase (ALP). Analyses for the change from baseline to the last visit that occurred on or before the date of treatment discontinuation and shift tables are described in Section 4.10.3. This section describes additional analyses for the topic.

The number and percentage of patients with the following abnormal elevations in hepatic laboratory tests will be summarized by treatment conditions. Fisher's exact test may be used to compare study interventions with placebo. Table 4.3 summarizes the analysis and period of analysis on Safety Analysis Set.

Table 4.3 Summary Tables and Figures Related to Hepatic Safety

Analysis	Analysis Period
Abnormal Postbaseline Categories – Hepatic Safety Parameters	Placebo-controlled treatment
 ALT: The number and percentage of participants with a measurement greater than or equal to 1 time (1X), 3 times (3X), 5 times (5X), 10 times (10X), and 20 times (20X) the performing lab upper limit of normal (ULN) during the treatment period for all participants with a postbaseline value. AST: The number and percentage of participants with a measurement greater than or equal to 1 time (1X), 3 times (3X), 5 times (5X), 10 times (10X), and 20 times (20X) the performing lab upper limit of normal (ULN) during the treatment period for all participants with a postbaseline value. ALP: The number and percentage of participants with a measurement greater than or equal to 2 times (2X), and 3 times (3X) the performing lab ULN during the treatment period will be summarized for all participants with a postbaseline. TBL: The number and percentage of participants with a measurement greater than or equal to 2 times (2X), 5 times (5X), and 8 times (8X) the performing lab ULN during the treatment period will be summarized for all participants with a postbaseline value. GGT: The number and percentage of participants with a measurement greater than or equal to 2 times (2X) the performing lab ULN during the treatment period will be summarized for all participants with a measurement greater than or equal to 2 times (2X) the performing lab ULN during the treatment period will be summarized for all participants with a postbaseline value. 	period and follow up period
Hepatocellular Drug-Induced Liver Injury Screening Plot (TBL vs ALT or AST)	Placebo-controlled treatment period
Hepatocellular Drug-Induced Liver Injury Screening Table	Placebo-controlled treatment period
Cholestatic Drug-Induced Liver Injury Screening Plot (TBL vs ALP)	Placebo-controlled treatment period
Cholestatic Drug-Induced Liver Injury Screening Table	Placebo-controlled treatment period

Abbreviations: ALP = alkaline phosphatase; ALT = alanine aminotransferase; AST = aspartate aminotransferase; GGT = gamma glutamyl transferase; TBL = total bilirubin; ULN = upper limit of normal.

Participant profiles will be created for participants meeting criteria for a comprehensive hepatic evaluation (as defined in the IMMA protocol) and are in Safety analysis set.

Participant profiles will include demographics, disposition, information collected on the hepatic safety CRFs (where applicable) and a display of study drug exposure, adverse events, medications, blood pressure, heart rate, and the liver -related measurements over time.

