7.1. Discontinuation of Study Intervention

Continuing in the study after discontinuation of study intervention

A participant who prematurely discontinues dosing with study intervention is strongly encouraged to remain in the study for safety monitoring through the treatment period and posttreatment follow-up as per ISA requirements.

See this master protocol (Section 8) and the relevant ISA (Section 1.3 [SoA] and Section 8) for data to be collected at the time of discontinuation from the study intervention and for activities in the posttreatment follow-up period and for any further evaluations that need to be completed.

Possible reasons for discontinuation of study intervention

The following reasons for early **permanent** discontinuation of study intervention apply to any ISA conducted under this master protocol.

Note: For laboratory values that meet early permanent discontinuation thresholds, the study intervention should be discontinued unless, in the opinion of the investigator, the laboratory abnormality is due to intercurrent illness or another identified factor. After consultation with the sponsor's designated medical monitor, the participant may be able to continue receiving study intervention. Laboratory tests may be repeated within 1 week to confirm whether discontinuation criteria have been met. Furthermore, if study intervention is not discontinued because of intercurrent illness, the investigator must confirm that the laboratory value no longer meets early discontinuation thresholds after the resolution of the intercurrent illness or other identified factor.

Hepatic event or liver test abnormality

The study drug should be interrupted or discontinued if one or more of these conditions occur:

Elevation	Exception
ALT or AST >8 times ULN	54
ALT or AST >5 times ULN for more than 2 weeks	
ALT or AST >3 times ULN and either TBL >2 times ULN or INR >1.5	In participants with Gilbert's syndrome, doubling of direct bilirubin should be used for drug interruption/discontinuation decisions rather than TBL >2 times ULN.

Elevation	Exception
ALT or AST >3 times ULN with the appearance of fatigue, nausea, vomiting, right upper quadrant pain or tenderness, fever, rash, and/or eosinophilia (>5%)	
ALP >3 times ULN, when the source of increased ALP is the liver	

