 and benefit information, required study treatment and posttreatment procedures, and the
 approximate probability of the participant's being randomized to the placebo control
 group.

Screening period:

The required screening period begins at Visit 1. Visit 1 must occur at least 3 days, but no more than 35 days, before the planned randomization visit (Visit 2).

A participant identification number will be assigned at Visit 1 if one was not assigned at Visit 601. Participant eligibility will be reviewed and confirmed by an eligibility review committee prior to random assignment to an ISA.

Study entry criteria

Participants found to be eligible according to all study entry criteria (See Sections 5.1 and 5.2 of Protocol IMMA) will be randomly assigned to one of the ISAs and will be randomly assigned to a treatment group within the designated ISA. The participant's within-ISA randomization treatment group assignment will be blinded. For some ISAs, additional entry criteria might be required prior to the second randomization. If so, these additional entry criteria will be specified in the relevant ISAs.

Randomization to ISAs

At the inception of this platform trial, only 1 ISA will be active. Eligible participants at the inception of the platform trial will be assigned only to that 1 active ISA.

As subsequent interventions enter the platform trial, the plan for randomization to active ISAs will be updated and explained in the new ISAs and/or other study documents.

Treatment and posttreatment periods

For investigations conducted under Master Protocol IMMA, the study treatment period begins at Visit 2. After the last visit in the treatment period, participants will have 1 or more posttreatment follow-up visits, as specified in the relevant ISA. See the ISAs for procedures conducted at Visit 2 and at subsequent visits in these study periods.

Early discontinuation of study intervention

Participants who permanently discontinue the study intervention early are encouraged to remain in the study for safety monitoring through the end of the study treatment period and to participate in posttreatment follow-up visits (see Protocol IMMA Section 7).

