4.3. Definition of Baseline and Postbaseline Measures

Baseline will be defined as the last available value before the first dose of the study intervention for both the efficacy and safety analyses, unless otherwise specified in the ISAs. In most cases, this will be the measure recorded at Visit 2.

The treatment period begins after the first study drug administration at Visit 2, unless otherwise specified in the ISAs. The end of the treatment period is specified in the ISAs. After the last visit in the treatment period, participants will have 1 or more posttreatment follow up visits, as specified in the ISAs. See the ISAs for procedures conducted at Visit 2 and at subsequent visits in these study periods.

Change from baseline will be calculated as the visit value of interest minus the baseline value. Percent change from baseline will be calculated as 100 times the change from baseline divided by the baseline.

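### SAP Table 4.3 gives two time windows for the hepatic elevation counts, and its joint liver-injury displays use a treatment period whose end is not tied to drug discontinuation

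*SAP*

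**What the plan says.** **Elevation counts.** In SAP Table 4.3 the ALT and AST lines count values "during the treatment period for all participants with a postbaseline value". The ALP, TBL and GGT lines limit themselves to the treatment period in almost the same terms. The Analysis Period cell beside these lines begins with the placebo-controlled treatment period and ends "period and follow up period".

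**Joint displays.** The same table lists a hepatocellular and a cholestatic screening plot, each with a companion table. All four carry the entry "Placebo-controlled treatment period", with no follow-up.

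**End of the period.** SAP 4.3 states: "The end of the treatment period is specified in the ISAs". SAP 1.2.1 says that participants who stop drug early are "encouraged to remain in the study for safety monitoring through the end of the study treatment period".

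**Other laboratory windows.** SAP 4.10.3 counts treatment-emergent high and low results "during the treatment period, and up to 60 days after treatment discontinuation".

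**Liver rules.** Protocol 7.1 states: "The study drug should be interrupted or discontinued if one or more of these conditions occur". Some of the listed conditions involve transaminases alone. Protocol 8.2.9 continues ALT, AST, ALP and TBL monitoring until values normalize or return to about baseline.

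**The concern.** There are two separate problems.

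First, the counts row contradicts itself. A programmer working from the row text would leave out follow-up values. One working from the column would include them. Both could claim to have followed the plan, and the by-arm numbers at each multiple of ULN could differ.

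Second, the screening displays exist to show a transaminase (or ALP) elevation together with a bilirubin elevation in the same participant. If ALT rises on treatment, drug is stopped, and TBL rises later, the joint picture is complete only at the later date. If that date lies outside the display window, the participant does not appear as a joint case. If the counts follow the column, the same participant could appear in both the ALT and the TBL counts of the same table, with nothing in the display that pairs them.

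**Working it through.** The plan gives no figure to reproduce here. The check compares sections, with some arithmetic for scale.

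**1. Is the contradiction an artefact of the PDF text?** The Analysis Period cell is broken across lines in the extracted text. The four display rows that follow name only the treatment period, so the follow-up words are particular to the counts row. The contradiction is in the plan.

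**2. Does the display window end at drug stop?** The SAP does not say.
- Ends at stop: SAP 4.10.3 cuts the box plots at the date of treatment discontinuation or completion. SAP 4.10.3.1 cuts the change to last visit at discontinuation, and SAP 4.10.5.1 does the same for QIDS-SR16. An analyst could carry that cut over.
- Continues after stop: SAP 4.3 leaves the end to the ISAs, and SAP 1.2.1 describes a treatment period that can outlast dosing. None of the cuts above is written for the screening displays.

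**3. How far apart are the two count windows in BT01?** Inputs: total ISA duration about 22 months and enrollment about 12 months (Protocol 1.1); treatment 24 weeks (Protocol 9.3.2.1); screening up to 5 weeks (Protocol 1.3).
- Weeks per month = 365.25 / 12 / 7 = 4.348.
- Treatment plus follow-up = (22 − 12) × 4.348 = 43.5 weeks.
- Follow-up = 43.5 − 24 = 19.5 weeks, a share of 19.5 / 43.5 = 45%.
- If 5 weeks of screening sit inside those 10 months: follow-up = 14.5 weeks, a share of 14.5 / 38.5 = 38%.

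Sixty days is 60 / 7 = 8.6 weeks, shorter than either follow-up estimate.

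**4. How often would a later bilirubin rise fall outside the display window?** This is an illustration on assumptions that are not in the documents: stop times uniform over 24 weeks, and a fixed lag L in weeks from stop to TBL rise. If the window runs to planned week 24, the share outside is L / 24.

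| Lag L (weeks) | Outside, window to week 24 | Outside, window ends at stop |
|---|---|---|
| 1 | 4% | 100% |
| 2 | 8% | 100% |
| 4 | 17% | 100% |
| 8 | 33% | 100% |

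The answer depends almost entirely on the undefined period end.

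**5. What does one case weigh?** BT01 has about 45 per arm (about 90 randomized 1:1). One case is 1 / 45 = 2.2%, with an exact one-sided 95% upper bound of 10.1%. No cases is 0%, with an upper bound of 1 − 0.05^(1/45) = 6.4%. This is for illustration only.

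**6. Where else would the case appear?**
- Participant profiles (SAP 4.10.3.1) show liver measurements over time, with no stated time limit, for anyone meeting the comprehensive hepatic evaluation criteria. With baseline TBL below 1.5 times ULN and no Gilbert's syndrome, Protocol 8.2.9 includes TBL of at least 2 times ULN among those criteria.
- The abnormal-laboratory listing (SAP 4.10.3) has no stated time limit.
- The high/low analysis (SAP 4.10.3) runs to 60 days after discontinuation, one analyte at a time.

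The first two are participant-level and the third is single-analyte. None shows ALT/AST or ALP jointly with TBL by arm.

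**The case against.** The strongest reply is that no case is lost. A reader might infer from Table 4.3 that bilirubin rises after a hepatic stop go unseen, or that they will most likely fall outside the plot. The documents support neither reading. The profiles, the listing and the 60-day analysis would show the case. A participant who stops drug but stays in the study may still be inside the treatment period, and Protocol 7.1 allows interruption, which need not end that period. The ISA and its SAP, which are not among the documents reviewed, may define the end. This part of the reply stands and limits the point to the by-arm joint displays.

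A second reply is that different windows can be deliberate. Protocol 6.5 lets standard-of-care therapy be resumed or modified after permanent discontinuation, which confounds later comparisons by arm. The high/low analysis uses the reference limit rather than multiples of ULN, so it is not a like-for-like standard. The master SAP also serves several interventions and lets ISAs override its safety analyses. These are fair reasons not to demand one identical window for every output. They do not explain why row text and column disagree, or why the display window is left undefined relative to last dose.

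**Conclusion.** The point holds in limited form. The contradiction in the counts row is certain from the text and needs correction whatever the ISA says. The gap in the screening displays is conditional: it arises if the period ends at drug stop, or if the joint elevation is completed after the planned end of treatment. What would then be absent is a joint case on the by-arm displays, not the case from the record.

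The 38% to 45% difference in post-baseline time rests on the protocol's approximate durations and applies to BT01 only. It measures time, not events. The documents give no hepatic event rate, so neither the chance of such a case nor its effect on a conclusion can be estimated.

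**What to change.** 1. **Counts.** Change the ALT, AST, ALP, TBL and GGT row text to match the Analysis Period column: treatment period plus follow-up period.
2. **Screening plots and tables.** Define the window relative to last dose so that it includes off-treatment values, at least to the 60 days after discontinuation already used in SAP 4.10.3. Because 60 days is shorter than the follow-up derived above, state both windows explicitly if they are to differ.
3. **Pairing.** State that the maximum ALT/AST (or ALP) is paired with the maximum TBL in that window, and mark off-treatment values with a distinct symbol.

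The cost is SAP wording and programming. Post-stop liver tests are already provided for in Protocol 8.2.9, and no clinical rule changes. The downside is that some elevations unrelated to drug will enter the plot; the symbol lets a reader identify them.

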
- [42] Have any of the following specific abnormalities on screening laboratory tests (Visit 1):
 - ALT or AST >2 times ULN
 - TBL ≥1.5 times ULN
 - hemoglobin <8.0 g/dL (<80.0 g/L)
 - total WBC <2500 cells/ μ L (<2.50 × 10³/ μ L or <2.50 GI/L)
 - neutropenia ANC <1000 cells/μL (<1.00 × 10³/μL or <1.00 GI/L)
 - lymphopenia ALC <500 cells / μ L (<0.50 × 10³/ μ L or <0.50 GI/L)
 - thrombocytopenia platelets $<50,000 \text{ cells/}\mu\text{L}$ ($<50 \times 10^3/\mu\text{L}$ or <50 GI/L)
 - eGFR (MDRD method) <45 mL/min/1.73 m² (FDA 2020).

Note: For repeat testing of screening laboratory tests, see Section 5.4.1.

- [43] Have known hypogammaglobulinemia or a screening (Visit 1) IgG level <565 mg/dL (<5.65 g/L).
- [44] Have other abnormal laboratory values at screening (Visit 1) which, in the opinion of the investigator, indicate unacceptable risk for the participant's safety in the study.
- [45] Have screening ECG abnormalities that, in the opinion of the investigator, are clinically significant and indicate an unacceptable risk for the participant's safety in the study.

Previous or concurrent clinical study experience

- [46] Have previously been randomized in any study investigating an intervention used in this study.
 - Note: Patients who received only placebo in a non-IMMA study (that is, not one of the ISAs of this master protocol) may be considered for enrollment if other study entry criteria are met.
 - See criterion [22] for patients who received at least 1 dose of investigational intervention in an ISA of this master protocol.
- [47] Are currently enrolled in any other clinical study involving an investigational product or any other type of medical research judged not to be scientifically or medically compatible with this study.

Other exclusions

- [48] Are largely or wholly incapacitated, permitting little or no self-care, such as being bedridden or confined to wheelchair.
- [49] Have donated more than a single unit of blood within 4 weeks before randomization (Visit 2) or intend to donate blood during the course of the study.
- [50] Have evidence of current or history within 1 year of any substance use disorder of any severity as defined by the DSM-V (APA 2013) in the opinion of the investigator, excepting disorders of nicotine or caffeine use.

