ALT or AST≥1.5 times ULN	ALT or AST ≥2 times baseline with hepatic signs/symptoms ^a or ALT or AST ≥3 times baseline
ALP ≥1.5 times ULN	ALP ≥2 times baseline

Abbreviations: ALP = alkaline phosphatase; ALT = alanine aminotransferase; AST = aspartate aminotransferase; TBL = total bilirubin; ULN = upper limit of normal.

At a minimum, this evaluation should include physical examination and a thorough medical history, as outlined above, as well as tests for PT-INR; tests for viral hepatitis A, B, C, or E; tests for autoimmune hepatitis; and an abdominal imaging study (for example, ultrasound or CT scan).

Based on the participant's history and initial results, further testing should be considered in consultation with the Lilly-designated medical monitor, including tests for HDV, CMV, EBV, acetaminophen levels, acetaminophen protein adducts, urine toxicology screen, Wilson's disease, blood alcohol levels, urinary ethyl glucuronide, and blood phosphatidylethanol. Based on the circumstances and the investigator's assessment of the participant's clinical condition, the investigator should consider referring the participant for a hepatologist or gastroenterologist consultation, MRCP, ERCP, cardiac echocardiogram, or a liver biopsy.

8.2.9.1. Additional Hepatic Data Collection in Participants Who Have Abnormal Liver Tests During the Study

Additional hepatic safety data collection in hepatic safety CRFs should be performed for participants who meet 1 or more of the following 5 conditions:

- Elevation of serum ALT to ≥5 times ULN on 2 or more consecutive blood tests (if baseline ALT <1.5 times ULN)
 - o In participants with baseline ALT ≥1.5 times ULN, the threshold is ALT ≥3 times baseline on 2 or more consecutive tests.
- Elevated TBL to ≥ 2 times ULN (if baseline TBL <1.5 times ULN) (except for cases of known Gilbert's syndrome)

^a Hepatic signs/symptoms are severe fatigue, nausea, vomiting, right upper quadrant abdominal pain, fever, rash, and/or eosinophilia >5%.

- In participants with baseline TBL ≥1.5 times ULN, the threshold should be TBL ≥2 times baseline.
- Elevation of serum ALP to ≥2 times ULN on 2 or more consecutive blood tests (if baseline ALP <1.5 times ULN)
 - In participants with baseline ALP ≥1.5 times ULN, the threshold is ALP ≥2 times baseline on 2 or more consecutive blood tests.
- Hepatic event considered to be an SAE
- Discontinuation of study drug due to a hepatic event (Section 7.1)

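### SAP Table 4.3 does not separate new from pre-dose elevations of ALP and GGT at multiples of ULN, which dilutes the between-arm comparison

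*SAP*

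**What the plan says.** Table 4.3 in SAP 4.10.3.1 lists 16 analyte-by-threshold counts: ALT and AST at 1, 3, 5, 10 and 20 times ULN, ALP at 2 and 3, TBL at 2, 5 and 8, and GGT at 2. Typical rows are "ALT: The number and percentage of participants with a measurement greater than or equal to 1 time (1X), 3 times (3X), 5 times (5X" and so on, "ALP: The number and percentage of participants with a measurement greater than or equal to 2 times (2X), and 3 times (3X" and "TBL: The number and percentage of participants with a measurement greater than or equal to 2 times (2X), 5 times (5X), and 8 times (8X". For ALT and AST, the denominator is given as "during the treatment period for all participants with a postbaseline value", and the other rows are worded to the same effect. No row refers to the baseline value. For these counts, "Fisher's exact test may be used to compare study interventions with placebo". SAP 4.10 describes a two-sided p-value of 0.05 or less as strong statistical evidence, while warning that safety p-values serve mainly as flags.

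Three other places bear on this:

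- **Entry limits.** Protocol 5.2, criterion [42], excludes "ALT or AST >2 times ULN" and TBL of 1.5 times ULN or more at Visit 1. It names no limit for ALP or GGT. For those, only investigator-judgment criteria such as [44] apply.
- **Treatment-emergent laboratory results.** SAP 4.10.3 does condition on baseline: "A treatment-emergent high result is defined as a change from a value less than or equal to the high limit at all baseline visits", followed by a value above that limit. It works at the reference limit only.
- **Protocol hepatic monitoring.** Sections 8.2.9 and 8.2.9.1 change the trigger when baseline is already raised. For extra hepatic data collection on ALP: "In participants with baseline ALP ≥1.5 times ULN, the threshold is ALP ≥2 times baseline on 2 or more consecutive blood tests".

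**The concern.** A participant who enters with ALP at 2.2 times ULN and stays there is counted in ALP ≥2X exactly like one who rises from normal to 2.5 times ULN on drug. Under the protocol's data-collection rule the first participant would need 2 × 2.2 = 4.4 times ULN on consecutive tests. The same participant therefore appears in Table 4.3 while meeting none of the protocol's baseline-relative ALP triggers.

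The other planned outputs do not close this gap for ALP and GGT. The treatment-emergent high count stops at 1 times ULN and leaves out anyone above the limit at baseline, so a rise in ALP from 1.3 to 2.5 times ULN is missed there. SAP 4.10.3.1 says that shift tables are described in 4.10.3, but that section describes only box plots, treatment-emergent counts and a listing. The liver-injury screening tables are named without definition. No described table therefore gives counts at ULN multiples by baseline status.

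At stake is the clarity of the between-arm hepatic comparison in an initial ISA of about 45 participants per arm. Unchanged elevations add the same expected background to both arms and shrink the visible contrast.

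**Working it through.** **Step 1: which rows can carry over a pre-dose elevation?** Compare each row's threshold with the Visit 1 entry limit in criterion [42].

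| Analyte | Entry limit (excluded) | Exposed rows | Largely protected rows |
|---|---|---|---|
| ALT | >2 × ULN | 1X | 3X, 5X, 10X, 20X |
| AST | >2 × ULN | 1X | 3X, 5X, 10X, 20X |
| ALP | none | 2X, 3X | none |
| TBL | ≥1.5 × ULN | none | 2X, 5X, 8X |
| GGT | none | 2X | none |

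Exposed: 1 + 1 + 2 + 0 + 1 = 5 of 16. Protected: 4 + 4 + 0 + 3 + 0 = 11 of 16. Protection is not absolute, because baseline is the last value before first dose (SAP 4.3) and can follow Visit 1 by up to 35 days. Of the five exposed rows, ALT and AST 1X have a baseline-conditioned counterpart in the treatment-emergent high analysis. That leaves three with none: ALP 2X, ALP 3X and GGT 2X.

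**Step 2: how much does carry-over dilute the contrast?** The documents give no elevation rates, so there is no planned figure to reproduce and all rates here are assumptions. From the documents: about 90 participants randomized 1:1, so 45 per arm, and a two-sided 0.05 flag. Let q be the share of each arm at or above the threshold at baseline who stay there, and let r be the rate of new elevations among the rest. Then the Table 4.3 proportion is

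P = q + (1 − q) × r.

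For q = 10%: placebo 0.10 + 0.90 × 0.02 = 11.8%; active 0.10 + 0.90 × 0.20 = 28.0%; risk ratio 28.0/11.8 = 2.4, against 0.20/0.02 = 10.0 for new elevations alone.

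Power is that of the two-sided Fisher's exact test, by enumerating both binomials. The restricted analysis uses 45 × (1 − q) per arm, rounded.

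| q | Table 4.3, placebo vs active (r = 2% vs 20%) | Risk ratio | Power as written | Power below threshold at baseline (n per arm) |
|---|---|---|---|---|
| 0% | 2.0% vs 20.0% | 10.0 | 73% | 73% (45) |
| 1% | 3.0% vs 20.8% | 7.0 | 69% | 73% (45) |
| 5% | 6.9% vs 24.0% | 3.5 | 52% | 70% (43) |
| 10% | 11.8% vs 28.0% | 2.4 | 39% | 64% (40) |

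With a smaller assumed effect (r = 2% vs 15%), power as written is 31% at q = 5% and 22% at q = 10%, against 42% and 36% restricted.

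**Step 3: does carry-over alone create false flags?** Set the new-elevation rate to zero in both arms. The chance that baseline alone separates the arms by three or more participants is 22% at q = 5% and 37% at q = 10%. Such a gap is not in itself a flag: 0 vs 3 of 45 gives p = 0.24, and 4 vs 7 gives p = 0.52. Fisher p ≤ 0.05 occurs in 0.6%, 2.0% and 2.5% of trials at q = 5%, 10% and 15%.

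**The case against.** The strongest reply is that the rows do what their title says. They are abnormal postbaseline categories, not treatment-emergent ones, and counting absolute ULN multiples matches the interruption and discontinuation table in protocol 7.1, which has no baseline condition. That is a good reason to keep the rows. It is not a reason to leave baseline status out of the comparison.

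Other baseline-aware outputs exist: change-from-baseline displays, the abnormal-findings listing, and participant profiles triggered by the protocol's baseline-relative criteria. These help in reading individual cases. They are not between-arm counts at ULN multiples, and protocol 8.2.9 sets no GGT threshold that would trigger a profile.

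A reader might infer three stronger things that the documents do not support:

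- **That all five analytes are affected alike.** The entry limits largely protect 11 of the 16 rows, including all of TBL.
- **That new elevations are masked.** Each one is still counted, and randomization balances carry-over in expectation. Only the contrast is diluted.
- **That baseline imbalance will produce false signals.** Step 3 shows that Fisher's test rarely flags it.

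It is also fair that the rates are assumed, that the test is optional, and that these analyses apply unless an ISA indicates otherwise. The ISA SAPs are not among the documents reviewed.

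**Conclusion.** The point holds for ALP ≥2X, ALP ≥3X and GGT ≥2X, where nothing limits the named analyte at entry and no described table separates new from carried-over elevations. It holds in a weaker form for ALT and AST ≥1X, which the treatment-emergent high analysis already covers. It does not extend in any material way to ALT/AST ≥3X or to TBL.

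The size depends on how many participants enter above the threshold, which the documents do not say. Under the assumed 20% against 2%, the power lost relative to the restricted count is 70 − 52 = 18 points at 5% carry-over and 64 − 39 = 25 points at 10% (rounded figures), but only about 4 points at 1%. The calculation also assumes that carried-over values stay above the threshold and that their share is the same in both arms. This is a gap in presentation and comparison that is worth closing. It does not invalidate the hepatic safety plan.

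**What to change.** Keep the current all-participant rows in Table 4.3. Add the same counts by maximum baseline category (at or below ULN; above ULN but below the row's threshold; at or above the threshold), for ALP and GGT first. Apply any Fisher's test for new elevations to participants below the threshold at baseline.

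That restricted count alone would drop participants who worsen from an already raised value. So also write out, in SAP 4.10.3, the shift tables that 4.10.3.1 cites, as maximum baseline to maximum postbaseline, and use them to show such worsening. The protocol 8.2.9.1 split is not a ready substitute: it has no AST or GGT rule, requires consecutive tests for ALT and ALP, and gives one threshold per analyte rather than one per row.

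The cost is SAP wording, a few more table rows from data already collected, and slightly smaller denominators in the tested rows (for example 43 or 40 instead of 45 per arm at 5% or 10% carry-over). No clinical rule changes. In the same edit, the section's opening could be aligned with its table, since the text names four analytes and Table 4.3 also lists GGT.
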